8 STUDY ASSESSMENTS AND PROCEDURES

8.1 FEASIBILITY ASSESSMENTS

At the time of recruitment to the study, participants' medical charts will be utilized to confirm the diagnosis of early pregnancy loss by ultrasound diagnosis. A HIPAA authorization form will be obtained from patients at the time of enrollment into the study, as EPL care will be documented in the UNC EPIC electronic medical record as well as in the study documentation. Any adverse events noted in the UNC EPIC electronic medical record during the study follow up time that are not associated with a study visit will be abstracted into the study documentation to appropriately follow up adverse events.

Once study participants have been approached, administration of UPA should occur within 14 days of diagnosis of early pregnancy loss, as over 50% of patients will have completion of their miscarriage with expectant management alone 14 days after diagnosis of early pregnancy loss [27]. Following administration of ulipristal acetate 90mg PO, participants will place misoprostol 800mcg vaginally 6 to 18 hours after ulipristal acetate. Study participants will note the time of misoprostol administration on their appointment card and report the time of misoprostol administration at their subsequent visit to ensure adherence to the study protocol.

Patients will return to clinic on day 3 for a transvaginal ultrasound to confirm absence of a gestational sac. Transvaginal ultrasound will be performed by an obstetrician/gynecologist (fellow or attending) in the UNC Family Planning Clinic to confirm absence of the gestational sac. These physicians have training in transvaginal ultrasound in early pregnancy. If participants are still noted to have a pregnancy in the uterus, they will be offered expectant management, medical management with an additional dose of 800mcg misoprostol, or surgical management with manual or electric uterine aspiration based on gestational age. Those patients with a pregnancy still in the uterus will return to clinic again on day 8 for an additional transvaginal ultrasound and again be offered options if pregnancy is still present. All patients will receive a phone call 30 days following misoprostol administration to assess for additional treatments needed, side effects, adverse events, and patient acceptability.

8.2 SAFETY AND OTHER ASSESSMENTS

At the time of diagnosis of EPL, the research coordinator will utilize the medical chart to review ultrasound images to confirm the diagnosis. Research personnel will then complete an eligibility questionnaire based on the inclusion and exclusion criteria as laid out above (5.1). Participants must be hemodynamically stable to take part in the study, which will be assessed by the OBGYN provider assessing the patient for their diagnosis.

On day 3 follow up, participants will provide information regarding the time and route they took their misoprostol medication to ensure compliance with the study activities. Patients will be informed in real time regarding their follow up transvaginal ultrasound results at their follow up visits, as they will be able to decide how they want to proceed with management (expectant management, additional medical management with second dose of misoprostol, or surgical management) if ultrasound still confirms the presence of an intrauterine pregnancy. Similarly, any patients who necessitated any additional care as part of their treatment of EPL (e.g. genetic studies on products of conception, infectious disease testing) will have those results shared in the standard manner for all patients seeking care with the Family Planning Division. Participants will report all adverse events (both pregnancy and non-pregnancy related) at each clinical visit.

During the two weeks post-treatment period, if women develop fatigue, malaise, abdominal pain or jaundice, a workup for liver injury should be performed. All patients with elevated LFTs (ALT, AST or total bilirubin) will be followed until resolution. For patients whose LFTs have not returned to normal within

one month, these patients will be referred to a specialist (e.g. hepatologist) for further workup and treatment if necessary.

The study sponsor will evaluate the first 20 patients for their post-treatment LFTs prior to expanding enrollment to the subsequent 20 patients.

Patients identified to have more severe medical adverse events or side effects will be advised to contact the UNC Family Planning Division. Based on the symptomatology and severity, patients will be instructed to seek care through the emergency department/urgent care or through the Family Planning Clinic. All medical adverse events or side effects will be managed based on the standard of care.

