1.3 SCHEDULE OF ACTIVITIES (SOA)

Procedures	Screening Visit 1, Day 0	Enrollment/Baseline Visit 1, Day 0	At Home Day 0	Study Visit 2 Day 3 +/- 1day	Study Visit 3 Day 8 +/- 1 day	Lab Testing Day 14 +/- 1 day	Study Visit 4 Day 30 +/- 7 days
Eligibility criteria	Х						
Informed consent	Х						
Demographics questionnaire	Х						
Administer UPA		Х					
Patient self-administers			Х				
misoprostol							
Physical exam	Х						
Vital signs	Х			Х	Х		
Hemoglobin and ABO/Rh testing	Х						
Liver function testing	Х					Х	
Adverse event review and evaluation	Х			х	Х		Х
Radiologic/Imaging assessment	Х			Х	Х		
Treatment success questionnaire completed by MD				Х	Х		
Offer additional intervention if needed if gestational sac still present				Х	Х		
Additional treatment questionnaire							Х
Side effects and adverse events questionnaire				х	х		Х
Patient acceptability questionnaire							Х

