- Participant is screened for eligibility by the study coordinator and offered admission to study if eligible
 - Review of radiologic imaging to confirm early pregnancy loss based on eligibility criteria
 - Review of physical exam findings and vital signs (heart rate, blood pressure, temperature) to ensure that patient is hemodynamically stable and not having an inevitable or incomplete abortion based on eligibility criteria
- Participant reviews and signs informed consent and HIPAA authorization form
- Participant completes paper baseline demographic questionnaire
- Participant will have hemoglobin, ABO/Rh status and liver function testing (ALT, AST, total bilirubin) if not already performed by primary OBGYN

 Participant takes 90mg ulipristal acetate with study team; given prescription for 800mcg misoprostol to take at home

Visit 2 (Day 3 ± 1 day):

- Participant returns to UNC Family Planning Clinic
- Participant has vital signs checked by RN at clinic
- Participant fills out questionnaire regarding bleeding symptoms and any side effects or adverse
 events after taking the ulipristal acetate and misoprostol, including reporting time and route of
 administration of misoprostol at home
- Participant has a transvaginal ultrasound completed by the principal investigator to ensure that the pregnancy has passed (no gestational sac visualized on ultrasound)
- If pregnancy is still in the uterus, patient will be offered surgical management, medical management (an additional dose of misoprostol 800mcg), or expectant management

Visit 3 (Day $8 \pm 1 \text{ day}$):

- Participant will only attend this visit if a gestational sac was still present on ultrasound on Visit
 2 and patient opted for medical management or expectant management. If gestational sac is absent at Visit 2, participant will not need Visit 3. All participants will complete Visit 4.
- Participant returns to UNC Family Planning Clinic
- Participant has vital signs checked by RN at clinic
- Participant fills out questionnaire regarding bleeding symptoms and any side effects or adverse events after taking the ulipristal acetate and misoprostol
- Participant has transvaginal ultrasound completed by the principal investigator to ensure that the pregnancy has passed (no gestational sac visualized on ultrasound)
- If pregnancy is still in the uterus, patient will be offered surgical management, medical management (if patient did not receive additional misoprostol at Visit 2), or expectant management

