 - If patient has medical management or expectant management, patient will be followed with weekly transvaginal ultrasounds until pregnancy has passed. No study questionnaires will be administered at these visits. Patient may elect for surgical management at any follow up visit as per the standard of care.

Lab Visit (Day 14 ± 1 day):

 Participant will have liver function testing (ALT, AST, total bilirubin) performed at outpatient laboratory

Visit 4 (Day 30 ± 7 days):

Participant will be called by the principal investigator to administer a follow up questionnaire
about any additional treatments taken to help pass the pregnancy, any side effects experienced
with the medication and participant acceptability

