8.3.5 ADVERSE EVENT REPORTING

Adverse event reporting by patient self-report will take place at each study visit, both in person and via telephone. Additionally, any adverse event that happens between study visits for which the participant seeks care at UNC Chapel Hill will be abstracted from the UNC EPIC electronic medical record. All adverse events will be recorded on case report forms (CRF) and will be reviewed by the principal investigator and mentor. Case report forms should be documented within 24 hours of the event, and review of the case report forms will occur on a weekly basis.

Likely mild medication side effects as detailed for UPA include headache (18%), nausea (12%), abdominal pain (12%). Other infrequent mild side effects include dysmenorrhea, fatigue and dizziness [14]. All patients may experience pain and discomfort during the process of pregnancy expulsion; however, this pain and discomfort are not different than what a patient would experience not in the study. Assessment of adverse events will include symptoms possibly related to the study medication and pregnancy expulsion, but will also include any additional adverse events experienced by the study participants.

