10.1.2 STUDY DISCONTINUATION AND CLOSURE

This study may be temporarily suspended or prematurely terminated if there is sufficient reasonable cause. Written notification, documenting the reason for study suspension or termination, will be provided by the suspending or terminating party to study participants, investigator, the Investigational New Drug (IND) sponsor and regulatory authorities. If the study is prematurely terminated or suspended, the Principal Investigator (PI) will promptly inform study participants, the Institutional Review Board (IRB), and sponsor and will provide the reason(s) for the termination or suspension. Study participants will be contacted, as applicable, and be informed of changes to study visit schedule.

Circumstances that may warrant termination or suspension include, but are not limited to:

• Determination of unexpected, significant, or unacceptable risk to participants

- Demonstration of efficacy that would warrant stopping
- Insufficient compliance to protocol requirements
- Data that are not sufficiently complete and/or evaluable
- A life-threatening medical situation with determined study procedure causality
- Persistent or significant incapacity as a result of study drug(s) or procedure(s)
- A study participant with hepatic enzyme elevation greater than 3 times the upper limit of normal seen on laboratory testing on day 14

Study may resume once concerns about safety, protocol compliance, and data quality are addressed, and satisfy the sponsor, IRB and/or Food and Drug Administration (FDA).

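### Women who skip Visit 3 are not asked about the Section 8.2 liver symptoms after Visit 2, and the one named liver suspension ground refers only to Day 14 tests

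*Combined protocol and SAP*

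**What the plan says.** - **Trigger.** Section 8.2: "During the two weeks post-treatment period, if women develop fatigue, malaise, abdominal pain or jaundice, a workup for liver injury should be performed". Elevated results are then followed until they resolve.
- **Scheduled liver tests.** The Schedule of Activities row "Liver function testing" is marked at screening and Day 14 only. Every participant is due the Day 14 test, with or without symptoms.
- **Planned symptom inquiry.** The row "Adverse event review and evaluation" is marked at screening, Visit 2 (Day 3 ± 1), Visit 3 (Day 8 ± 1) and Visit 4 (Day 30 ± 7). The side-effect questionnaire is marked at Visits 2, 3 and 4. Both are blank in the Day 14 column.
- **Visit 3.** Section 4.1: "If gestational sac is absent at Visit 2, participant will not need Visit 3". Women who choose surgical management at Visit 2 do not attend it either.
- **Day 14.** Section 4.1: "Participant will have liver function testing (ALT, AST, total bilirubin) performed at outpatient laboratory". No symptom inquiry is described.
- **Expected symptoms.** Section 8.3.5 lists abdominal pain (12%) and, less often, fatigue as effects of ulipristal, and adds: "All patients may experience pain and discomfort during the process of pregnancy expulsion".
- **Liver suspension ground.** Section 10.1.2 names "A study participant with hepatic enzyme elevation greater than 3 times the upper limit of normal seen on laboratory testing on day 14" in a list of circumstances that may justify suspension or termination and that is expressly not exhaustive.

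**The concern.** The trigger runs for two weeks, but for women who skip Visit 3 the planned questions stop in the first days of that period and resume after it has closed. The Day 14 test would show an enzyme rise still present on that day. A rise that came and went earlier would be found only through a symptom-driven work-up, and no planned contact prompts for one after Visit 2.

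The named symptoms add to the difficulty. Pain and fatigue are expected here, and Section 8.2 does not say whether expected symptoms count. If staff discount them, the trigger rests on malaise and jaundice, which the Section 9.4.3 list does not name. If staff count them, work-ups will follow from ordinary drug effects.

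The suspension ground is a separate mismatch. Section 8.2 produces liver results on days other than Day 14, and the named ground does not mention them. Liver injury is the risk for which the protocol added baseline and Day 14 tests, a sponsor review after 20 patients and a suspension ground, so these parts should fit together.

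**Working it through.** The plan gives no figure to reproduce. The check lays the contact schedule over the trigger period, counting Day 0 as the day of ulipristal and Day 14 as the last trigger day.

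**Inputs.** Visit 2 falls on Day 2 to 4, Visit 3 on Day 7 to 9, the laboratory draw on Day 13 to 15 and Visit 4 on Day 23 to 37 (Schedule of Activities). The target is 40 participants (Section 7.2). The abdominal pain rate is 12% (Section 8.3.5).

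**1. Trigger days after the last planned inquiry = 14 − day of last inquiry.**
- Visit 3 skipped: 14 − 4 = 10 to 14 − 2 = 12 days, or 71% to 86% of the period (nominally 14 − 3 = 11 days).
- Visit 3 attended: 14 − 9 = 5 to 14 − 7 = 7 days, or 36% to 50%. Later weekly ultrasound visits carry no study questionnaires (Section 4.1).

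**2. Gap from Visit 2 to the next planned inquiry when Visit 3 is skipped.** Shortest 23 − 4 = 19 days, nominal 30 − 3 = 27, longest 37 − 2 = 35. Section 8.3.4 says that the Day 30 call solicits only bleeding and infection events of a stated severity as adverse events. The side-effect questionnaire is also given then, but after the trigger period has ended.

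**3. How many women.** The documents give no expected share skipping Visit 3. Assuming 50% to 90%, the longer gap applies to 0.5 × 40 = 20 up to 0.9 × 40 = 36 women.

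**4. Trigger symptoms against the Section 9.4.3 list.** Fatigue is named. Malaise and jaundice are not. Abdominal pain is not named as such; the nearest entries are severe cramping and a residual other category.

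**5. Expected symptoms meeting the trigger (illustration).** At 12%, 0.12 × 40 = 4.8 women would report abdominal pain. The chance of at least one among the first 20 is 1 − 0.88^20 = 0.92. The 12% comes from the trials behind the emergency contraception approval (Section 2.3.1). It is not shown to apply at the study dose and leaves out pain from misoprostol and expulsion.

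**6. Liver results against the suspension ground.** Section 8.2 yields work-ups before Day 14 and repeat tests after it. A result above 3 times the upper limit on, say, Day 7 or Day 21 does not literally meet the named ground. Other provisions have no day limit:
- the general unacceptable-risk ground (Section 10.1.2);
- the temporary stop at the first severe adverse event (Section 8.3.6);
- expedited reporting of Hy's law cases (Section 8.3.6);
- the sponsor's review of post-treatment liver tests in the first 20 patients (Section 8.2).

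**The case against.** A reader might infer that the trigger cannot work at all. The documents do not support that. At Visit 2, "Participant fills out questionnaire regarding bleeding symptoms and any side effects or adverse" events after treatment, and this applies to every participant. Visit 3 repeats it for a subset. Between visits there are a chart alert, abstraction of care sought at the same institution, and advice to contact the clinic for more severe events. The wording of Section 8.2 is not tied to a scheduled contact, and all women are due the Day 14 test anyway. This limits the point to active ascertainment. The unscheduled routes depend on a woman seeking care or judging herself more severely affected.

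A reader might also infer that malaise and jaundice are never asked about. Section 9.4.3 is an analysis list with an other category. The questionnaire is not in the documents, and Visit 2 covers any side effect. The supportable statement is that these symptoms are not named items in the list. Nor do the documents show that the trigger would be met in most women; the only rate available gives about 5 of 40.

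Sections 8.3.4 and 8.3.5 place adverse event inquiry at each study visit. That is not a clear contradiction of the blank Day 14 cell. The retention outcome counts Days 0, 3/8 and 30 as the study visits, and the schedule heads Day 14 as laboratory testing, while Sections 4.1 and 7.3 call it a visit. It is a labelling ambiguity.

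Finally, it is tempting to read Section 10.1.2 as putting an early enzyme rise beyond suspension. It does not: the list is permissive and open, and even a Day 14 rise compels nothing. The other provisions help without fully replacing a named ground. Hy's law is a reporting duty, the 20-patient review states no criterion, and the severe-event stop turns on severity, which Section 8.3.3.1 defines largely by effect on daily activity.

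**Conclusion.** The concern holds in limited form. For women who skip Visit 3, the Section 8.2 symptoms are not actively ascertained after Visit 2. That leaves 10 to 12 of the 14 trigger days and a gap of 19 to 35 days to the next planned inquiry. These figures rest only on the visit windows and on counting from Day 0; counting from misoprostol, up to 18 hours later, would extend the period by at most a day. The number of women affected (20 to 36 of 40) rests on an assumed share.

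Two matters need reconciling: whether the pain and fatigue that Section 8.3.5 treats as expected count under Section 8.2, and which liver tests the suspension ground in Section 10.1.2 covers. A large rise on another day is left to discretion, not excluded. No outcome estimate or sample size depends on any of this. It is a gap in safety ascertainment that is cheap to close.

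**What to change.** Mark adverse event review and the side-effect form in the Day 14 column of the Schedule of Activities. Study staff can give the form by telephone, or it can be completed on paper at the draw. Include items covering each symptom named in Section 8.2. State the same in Sections 4.1 and 8.3.5, so that it is clear whether Day 14 counts as a visit for adverse event inquiry.

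The first inquiry after Visit 2 would then come 13 − 4 = 9 to 15 − 2 = 13 days later, instead of 19 to 35. It would ask about the trigger period at or near its end and place symptoms beside the liver result. It would not bring a work-up forward to the days before the draw, so the unscheduled routes still matter.

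The sponsor should reconcile Section 8.2 with 8.3.5 on expected symptoms, and Section 8.2 with 10.1.2 on which liver tests the suspension ground covers. No clinical or stopping rule is proposed here.

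The cost is one short form or call per woman at an existing contact, items for malaise, jaundice and abdominal pain where the form lacks them, and slightly more adverse events recorded.

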2 INTRODUCTION

2.1 STUDY RATIONALE

Early pregnancy loss affects approximately 10% of women throughout their reproductive lives [1]. Options for management of early pregnancy loss include expectant management, medical management, or surgical management. Data from two large randomized controlled trials suggests that pretreatment with mifepristone 200mg, a selective progesterone receptor modulator, prior to administration of misoprostol 800mcg increases effectiveness of medical management of early pregnancy loss and decreases the need for subsequent surgical management [2,3]. However, mifepristone is subject to regulations based on the FDA Risk Evaluation and Mitigation Strategy (REMS) restrictions that have remained in place for more than 20 years despite extensive safety data for mifepristone and evidence-based protocols for its use. Many OBGYN and non-OBGYN providers do not prescribe mifepristone due to these logistical barriers. Ulipristal acetate (UPA) is another selective progesterone receptor modulator that may allow for similar priming of the endometrium and sensitization of the myometrium to the prostaglandins to improve effectiveness of misoprostol in medical management of early pregnancy loss.

Ulipristal acetate is not subject to the FDA REMS restrictions and is available as a prescription medication through commercial pharmacies, with approximately 72% of pharmacies able to fill the prescription within 24 hours [4]. Thus, utilizing UPA plus misoprostol for early pregnancy loss may improve access to patients who otherwise may not be prescribed mifepristone. We propose a pilot feasibility study of UPA plus misoprostol for medical management of early pregnancy loss to assess if a larger clinical trial would be possible.

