similar clinical scenarios ranging from contraception to treatment of fibroids, endometriosis, and other causes of heavy or irregular bleeding. In the normal menstrual cycle, progesterone from the corpus luteum transforms the proliferative endometrium to the secretory endometrium for implantation. In contrast, the presence of SPRMs causes the endometrium to undergo glandular dilation and antiproliferative effects [18]. Like other SPRMs, UPA induces changes in the endometrium including a significant increase in glandular dilation and architecture and decrease in endometrial thickness similar to the effects noted following administration of mifepristone [19,20]. UPA's effect on endometrial cells is also responsible for similar changes in receptivity markers when compared to mifepristone [21,22]. With the similarities between UPA and mifepristone, a recent pilot study investigated UPA in place of mifepristone for cervical preparation prior to dilation and evacuation for termination of pregnancy between 16- and 18-weeks' gestation and found that UPA was a feasible and acceptable alternative [23].

While mifepristone is an effective medication for EPL, prescribing restrictions limit the ability of patients to use this medication to increase the efficacy of medical management of EPL. Thus, alternative regimens are needed to increase access to effective medical management of EPL for women choosing medical management. Given similarities between UPA and mifepristone, we propose utilizing UPA prior to misoprostol for medical management of EPL. As no prior studies have investigated UPA for this use, we propose a pilot feasibility study of UPA plus misoprostol for medical management of EPL to inform a subsequent larger clinical trial if successful.

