Once early pregnancy loss has been diagnosed on ultrasound, patients are referred back to their primary OBGYN provider for counseling on the diagnosis and discussion of management options, often on the same day as the ultrasound. Patients desiring medical management of EPL are referred to the GYN consultation team at UNC via a telephone call for more information regarding medical management and prescription of the requisite medications. The GYN consultation team will offer patients the standard of care of mifepristone and misoprostol versus admission into the study for ulipristal acetate and misoprostol. Patients interested in the study will then be approached by the research staff. Patients who initially elect for expectant management of their early pregnancy loss but desire medical management at a later date may be offered admission into the study as well within the first two weeks following diagnosis, as over 50% of patients will pass their pregnancy after two weeks following diagnosis [27].

Thus, patients approached for participation will meet the following criteria:

- Diagnosed with early pregnancy loss or anembryonic gestation between 5- and 12-weeks' gestation on viability ultrasound at UNC Chapel Hill OBGYN clinics and UNC Chapel Hill Emergency Department
- Desire medical management of early pregnancy loss and are clinically stable to do so (not hemodynamically unstable or with active vaginal bleeding)
- Interested in learning more about the study from research team

To aid in recruitment efforts, flyers will be placed in each of the two recruitment locations and brochures will be offered to patients if they are considering admission to the study but need time to process their diagnosis. All flyers and brochures will have contact information for the study team so

patients can reach out to the research team directly. Provider flyers will also be placed in the provider workspaces at both recruitment locations and in the GYN workspace at UNC Chapel Hill where the GYN consultation team is based to provide detailed information on the study and eligibility requirements. All study materials will be written to an appropriate reading level to ensure comprehension among all potential participants.

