9.4.6 PLANNED INTERIM ANALYSES

Given the small size and short duration of the study, no interim analysis will be completed.

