10.1.6 SAFETY OVERSIGHT

Safety oversight will be under the direction of a medical monitor with appropriate expertise given the small number of participants in the study. The medical monitor should be independent from the study conduct and free of conflict of interest, or measures should be in place to minimize perceived conflict of interest. The medical monitor will review this project at least semiannually to assess safety and efficacy data of the study. At this time, each data element that the medical monitor needs to assess will be clearly defined. The medical monitor will provide its input to the study sponsor and study team.

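### Participants forgo the site's mifepristone regimen for one untested in early pregnancy loss, but the risk text omits this and the pause at 20 participants reviews only liver tests, with no criterion for lack of effect

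*Combined protocol and SAP*

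**What the plan says.** **What is given up.** Section 5.5: "The GYN consultation team will offer patients the standard of care of mifepristone and misoprostol versus admission into the study". Section 2.1 says that mifepristone pretreatment "increases effectiveness of medical management of early pregnancy loss and decreases the need for subsequent surgical management". On UPA, section 2.2: "As no prior studies have investigated UPA for this use, we propose a pilot feasibility study of UPA plus misoprostol".

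**How the risk is described.** Section 2.3.1 covers drug side effects, blood draws, confidentiality, stigma, and the time and income lost to in-person follow-up. It does not mention that the regimen may clear the pregnancy less often than the one forgone. Section 2.3.3 argues that all participants receive misoprostol, which is standard in settings where mifepristone is not prescribed. The end of 5.5 says that study procedures match standard care at the site, so that taking part carries no risk of care that differs.

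**How enrolment is gated.** Section 8.2: "The study sponsor will evaluate the first 20 patients for their post-treatment LFTs prior to expanding enrollment to the subsequent 20 patients". Section 9.4.6: "Given the small size and short duration of the study, no interim analysis will be completed". Section 10.1.2 opens its list with "Circumstances that may warrant termination or suspension include, but are not limited to". That list includes "Demonstration of efficacy that would warrant stopping" and a day-14 liver enzyme threshold, but not lack of effect. Under 8.3.6 the first severe adverse event pauses the study. Section 10.1.6: "The medical monitor will review this project at least semiannually to assess safety and efficacy data of the study". The same section leaves the monitor's data elements to be defined at the time of review.

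**The concern.** A patient who enters the study exchanges a regimen that the protocol itself describes as more effective than misoprostol alone for one with no data in this condition. A lower clearance rate is therefore a foreseeable risk. It belongs in the risk section and is a natural subject for the one planned halt in enrolment.

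As written, the halt can be passed on liver tests alone, however many of the first 20 still have a sac at day 3. Repeat misoprostol and aspiration are listed in 9.4.3 under resolution rather than adverse events, so a run of retained sacs need not set off the severe-event pause either. What is at stake is more repeat dosing, aspiration or waiting among the second 20 participants, and a risk description that does not match what the site offers.

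**Working it through.** **1. The text on usual care.** Three statements do not fit together.
- 5.5 (recruitment) and 2.3.1: usual care here is mifepristone plus misoprostol, generally followed up by telephone.
- 5.5 (end): no risk of care that differs. But the study replaces mifepristone with UPA and adds in-person visits.
- 2.3.3: misoprostol alone is standard where mifepristone is not prescribed. By 5.5, this site is not such a setting.

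**2. Planned enrolment and timing.** The plan's 40 comes from about 100 diagnoses a year and a prior ratio of 300/800 (9.2). 100 × 300/800 = 37.5, and 2 per week × 52 = 104, with 104 × 0.375 = 39. The stated 40 is reproduced to within about 2 patients. At 40 in 12 months, evenly spread, participant 20 arrives at about 20/40 × 12 = 6 months. A semiannual monitor review therefore falls near the gate on the planned schedule, but nothing in 8.2 or 10.1.6 links the two.

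**3. Are the data ready at the pause?** The schedule of activities puts the scan at day 3 ± 1 and the liver test at day 14 ± 1. Every scheduled day-3 scan precedes the liver result that the pause already awaits.

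**4. Size, under assumed rates.** The documents give no clearance rate for UPA, for mifepristone plus misoprostol or for misoprostol alone. I assume usual care clears 80% by day 3 (range 70% to 85%) and vary UPA's true rate p. For illustration, review is prompted if X ≤ 11, where X ~ Binomial(20, p) and scans are complete.

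- Excess retained sacs in the second 20 = 20 × (reference − p).
- Expected number avoided, only if the review ends enrolment = that excess × P(X ≤ 11).

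| True p | P(X ≤ 11) | Excess at reference 70% / 80% / 85% | Avoided at 70% / 80% / 85% |
|---|---|---|---|
| 40% | 94% | 6 / 8 / 9 | 5.7 / 7.5 / 8.5 |
| 50% | 75% | 4 / 6 / 7 | 3.0 / 4.5 / 5.2 |
| 60% | 40% | 2 / 4 / 5 | 0.8 / 1.6 / 2.0 |

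For example, at p = 50% and an 80% reference: 20 × 0.30 = 6, and 6 × 0.748 = 4.5. At a true 70% or 80% the prompt fires with probability 11% or 1%.

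**5. Limits of 20 scans.** 11 of 20 has an exact 95% confidence interval of 32% to 77%. A true 60% is missed 60% of the time. If 10% of scans are missing and counted as not cleared, X ~ Binomial(20, 0.9p), and the prompt fires with probability 30% or 8% at a true 70% or 80%. Applying 55% or fewer to scanned participants only lowers these to 8.5% and 0.8%, but detection at a true 40%, 50% or 60% falls to 90%, 66% or 32%.

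**The case against.** The strongest reply is that effectiveness is already watched. The study is open-label at one site. The principal investigator does most of the scans (10.1.7), so a very low clearance rate would be seen as it happened. The independent monitor receives efficacy data, on the planned schedule at about participant 20, and the suspension list is open-ended. Each retained sac found at day 3 or day 8 is met with an offer of further treatment (4.1). All of this stands. A reader might infer that nobody looks at effectiveness, or that the study could not be halted for lack of effect; the documents support neither. What remains is narrower: the monitor's review is not tied to the gate, its content is not yet defined, and no criterion is set. Treatment of retained sacs limits harm to each participant but not the number exposed.

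A second reply is that this is a 40-person feasibility pilot whose secondary outcomes are for generating hypotheses (9.1) and which plans no formal testing (9.4.1), so a futility boundary is a matter of preference. That stands against requiring a particular cut-off. With an adherence target of only more than 50%, a low count could also reflect mistimed misoprostol rather than UPA. It does not stand against looking at data already in hand, which is participant protection and not a hypothesis test.

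Third, 2.3.3 openly says that mifepristone raises effectiveness, and each patient is offered it as the alternative. This is fair, but it does not put the risk into 2.3.1 or remove the conflict in 5.5. A reader might go further and infer that participants are misinformed. The consent pages are not in the reviewed text, so that cannot be judged.

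**Conclusion.** The point holds and should be acted on, though it does not invalidate the study. The wording conflict in 5.5 and the omission in 2.3.1 rest on the text alone. So does the finding that the only formal gate before participant 21 concerns liver tests, with no criterion for lack of effect.

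The size rests on assumed rates. At an 80% reference and a true UPA rate of 40% to 60%, continuing would mean 8 to 4 more retained sacs in the second 20 (6 to 2 at a 70% reference, 9 to 5 at 85%). The figures for sacs avoided further require complete scans and a review that actually ends enrolment, so they do not predict the benefit of a non-binding look. It is tempting to conclude that the plan must carry a numeric futility rule. The documents do not support that for a hypothesis-generating outcome, and 20 scans can flag a large shortfall but not reliably a modest one.

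**What to change.** - **8.2:** at the existing pause, have the sponsor and medical monitor also review day-3 sac absence in all of the first 20 who took UPA, before enrolment resumes. Show adherent participants and missing scans separately.
- **9.4.6:** note this look.
- **10.1.6:** name day-3 sac absence as a data element for the monitor.
- **10.1.2:** add lack of effectiveness to the list.
- **2.3.1:** list forgoing mifepristone, with possibly more further treatment, as a risk.
- **5.5:** replace the closing assurance about care with a statement that UPA takes the place of mifepristone and that in-person visits are added.
- **Optional:** a non-binding numeric prompt, chosen by the sponsor against a stated reference rate, with a rule for missing scans. The 11-of-20 cut-off above is only an illustration.

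The cost is a possible short delay while the review takes place. No visits or data are added, and the sample size and primary outcomes are unchanged. If a numeric prompt is adopted, unnecessary reviews are an added cost; for the illustrative cut-off, their chance is shown in the working.
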